Appendix D. BI-RADS Classification Previously read:

[figure not shown]
The BI-RADS assessment categories are:

- 0 -Incomplete,
- 1 Negative,
- 2 Benign findings,
- 3 Probably benign,
- 4 Suspicious abnormality,
- 5 Highly suspicious of malignancy,
- 6 Known biopsy with proven malignancy

Has been changed to read:

The BI-RADS assessment categories are:

- 0 -Incomplete,
- 1 Negative,
- 2 Benign,
- 3 Probably benign,
- 4 Suspicious,

- 5 Highly suggestive of malignancy,
- 6 Known biopsy proven malignancy

Reference: ACR BI-RADS Atlas Fifth Edition. p. 15-8. Available from: https://www.acr.org/~/media/ACR/Documents/PDF/QualitySafety/Resources/BIRADS/01-Mammography/02--BIRADS-Mammography-Reporting.pdf?la=en.¹²

3.0 Introduction

This statistical analysis plan (SAP) describes the planned statistical analyses for elagolix (ABT-620) Study M12-815 titled "A Phase 3 Study to Evaluate the Efficacy and Safety of Elagolix in Combination with Estradiol/Norethindrone Acetate for the Management of Heavy Menstrual Bleeding Associated with Uterine Fibroids in Premenopausal Women." The analysis plan was created based on the Study Protocol M12-815 Amendment 3 dated 25 September 2017.

This analysis plan describes both the efficacy and safety analyses. The pharmacokinetic data will be analyzed separately and is not addressed in this SAP.

The SAS System 9.2 or above will be used to perform the statistical analyses. All statistical tests will be two-sided and a significance level of 0.05 will be used unless otherwise specified.

4.0 Study Objectives, Design and Procedures

4.1 Objectives

The objectives of this study are to:

- Assess the efficacy, safety and tolerability of elagolix 300 mg BID in combination with E2/NETA (estradiol 1 mg/norethindrone acetate 0.5 mg QD), versus placebo to reduce heavy menstrual bleeding (HMB) associated with uterine fibroids in premenopausal women 18 to 51 years of age.
- The study will also characterize the impact of E2/NETA on the safety/tolerability (including bone mineral density [BMD] and other hypoestrogenic side effects) and efficacy of elagolix.

4.2 Study Design

This Phase 3, randomized, double-blind, multicenter, placebo-controlled study is designed to evaluate the efficacy, safety and tolerability of elagolix alone and in combination with

E2/NETA in the management of premenopausal women with HMB associated with uterine fibroids. Approximately 400 subjects will be randomized in a 1:1:2 ratio to 1 of the following 3 treatment groups:

- placebo (n = 100)
- elagolix 300 mg BID (n = 100)
- elagolix 300 mg BID plus E2/NETA (estradiol 1 mg/norethindrone acetate 0.5 mg) QD (n = 200)

[figure not shown]
This study is designed to enroll approximately 400 subjects across approximately 125 clinical study sites to meet scientific and regulatory objectives without enrolling an undue number of subjects in alignment with ethical considerations.

The study consists of 4 periods as follows:

1. Washout Period prior to Screening (if applicable)
2. Screening Period of approximately 2.5 to 3.5 months prior to first dose of study drug
3. 6-month Treatment Period
4. 12-month Post-Treatment Follow-up Period (OR Subjects may enter an extension study [Study M12-816] if they are willing and qualify, based on safety parameters, to receive an additional 6 months of treatment, followed by 12 months of follow-up).

Subjects will visit the site for assessments and testing during the Washout Period, if applicable, during the Screening Period (Initial Screening Visit, Screening Product Collection Visits [PCVs] for assessment of menstrual blood loss) and Treatment Period (Day 1 [Randomization] and monthly during Month 1 through Month 6). Following the 6-month Treatment Period, subjects will enter into a 12-month Post-Treatment Follow-up Period or an extension study. The Study Periods are illustrated in [Figure 1](#).

Figure 1. Study Schematic

4.3 Sample Size

Approximately 400 subjects will be randomized in a 1:1:2 ratio to placebo (N = 100), elagolix 300 mg BID (N = 100), or elagolix 300 mg BID plus E2/NETA (N = 200). The sample size will provide at least 90% power to detect a difference between the elagolix 300 mg BID plus E2/NETA group and the placebo group in the percentage of subjects with menstrual blood loss (MBL) volume < 80 mL during the Final Month (as defined in Section 7.2) and 50% or greater reduction in MBL volume from Baseline to the Final Month under the assumption of responder rates being 60% and 30% for elagolix 300 mg BID plus E2/NETA and placebo, respectively. The sample size determination is primarily driven by the need for a sufficient number of patients for the safety database. The above sample size was calculated using nQuery advisor 7.0.

4.4 End-of-Treatment Period Analysis

An end-of-treatment period analysis of the primary and secondary efficacy variables along with demographic and safety variables will be performed after the last subject completes the 6-Month Treatment Period of Study M12-815. This end-of-treatment period analysis will include all treatment period data from all patients randomized into the study. The data base will be versioned and any discrepant data will be clarified before the lock. Analyses will be performed by an external Independent Data Analysis Center (IDAC).

Subjects completing Study M12-815 are eligible to be enrolled in the double-blind extension study. The blinding at the subject level for the extension study will be maintained as the efficacy data analyses will only present overall treatment group results to the sponsor. The sponsor will have access to the unblinded results at the treatment group level. However, the blinded data at the subject level will not be included in the results of the demographic, efficacy, or safety endpoints provided to the sponsor. The randomization schedule for Study M12-815 will be provided to the IDAC by someone other than the project statistician, who is otherwise not involved with this study. All AbbVie study personnel will remain blinded until the blind is broken for the double-blind extension study. The end-of-treatment period analysis will only include data collected during the 6-month treatment period of the study and will not include data collected during the Post-Treatment Follow-up Period.

Since this end-of-treatment period analysis is the only and final analysis of the primary and ranked secondary endpoints of Study M12-815, no adjustment of alpha-level is necessary.

5.0 Analysis Populations

5.1 Definition for Analysis Populations

Full Analysis Set

The full analysis set is comprised of all randomized subjects who have received at least one dose of study drug in this study. The data from the full analysis set will be presented by the treatment group assigned at the time of randomization, even if the subject does not receive the correct treatment or does not follow the protocol until completion. The full analysis set will be used for all Baseline and efficacy analyses.

Safety Analysis Set

The Safety Analysis Set will include all randomized subjects who received at least one dose of study drug. The data from the safety analysis set will be presented by the treatment group as treated, independent of treatment group assignment at the time of

randomization. If a subject receives more than one treatment, she will be analyzed in the treatment group to which she was randomized. The Safety Analysis Set will be used for all safety analyses.

5.2 Variables Used for Stratification of Randomization

There is no variable used for stratification of randomization.

6.0 Protocol Deviation and Enrollment into Extension Study

Protocol deviations will be summarized and listed by treatment group. The number and percentage of subjects not enrolling into the extension study, and the reason for not enrolling into the extension study will be summarized by treatment group.

7.0 Analysis Conventions

7.1 Definition of Baseline

Unless otherwise specified below, Baseline for a variable will be defined as the last non-missing value obtained prior to or on Study Day 1.

MBL Volume Baseline

Baseline MBL volume will be defined as the mean of total MBL volume from all the qualified menstrual cycles during the Screening Period, in which the total MBL volume is from all validated and non-validated sanitary products that subjects returned and where the MBL volume of validated sanitary products only (excluding non-validated sanitary products) is greater than 80 mL. All menstrual cycles during the Screening Period in which the total MBL of all validated products is less than or equal to 80 mL will not be included in the Baseline MBL volume calculation. If the gap between two consecutive Screening menstrual cycles is 1 day apart or less (i.e., out of the two consecutive cycles, the start date of the second cycle – the end date of the first cycle ≤ 2), these two Screening menstrual cycles will be combined as one Screening menstrual cycle for the calculation of Baseline.

Bleeding Days Baseline

Baseline for bleeding days (as defined in Section 7.6) will be the mean of total number of bleeding days over all the qualified Screening menstrual cycles that are used to calculate Baseline MBL volume.

Fibroid and Uterine Volume Baseline

Baseline for uterine volume, volume of the largest fibroid, total fibroid volume (3 largest fibroids), and endometrial thickness measured by ultrasound (transvaginal [TVU] or transabdominal [TAU]) or Magnetic Resonance Imaging (MRI) will be based on the last non-missing measurement collected during the Screening Period. If there is no measurement collected on or prior to Study Day 1, the first measurement collected prior to Study Day 8 (Study Day 8 is not included) will be used as Baseline.

Adenomyosis Baseline

Baseline for adenomyosis measured by TVU/TAU or MRI will be based on the last non-missing measurement collected on or prior to Study Day 1. If there is no measurement collected on or prior to Study Day 1, the first measurement collected prior to Study Day 15 (Study Day 15 is not included) will be used as Baseline.

Quality of Life Questionnaires Baseline

Baseline for quality of life questionnaires including Uterine Fibroid Symptom Questionnaire (UFS-QoL), EuroQoL-5D (EQ-5D-5L) questionnaire, Work Productivity and Activity Impairment (WPAI) questionnaire and Health Care Resource Utilization (HCRU) questionnaire will be based on the measurement collected on or before Study Day 1. For UFS-QoL, EQ-5D-5L and HCRU, if there is no measurement collected on or before Study Day 1, the first measurement collected prior to Study Day 8 (Study Day 8 is not included) will be used as Baseline.

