Subjects awaiting test results to determine eligibility into the extension study may be required to remain in the Treatment Period to receive additional study drug until results become available. Visits associated with this waiting period will be documented as Unscheduled Visits and subjects will continue to undergo study-related assessments and procedures as outlined in Appendix C and Section 5.4.4 Delays in Rollover into the Extension Study.

Visit Windows

Visit windows will be allowed for the monthly visits during the Treatment and Post-Treatment Follow-Up Periods. Each subsequent monthly visit should be scheduled based on the date of the Day 1 (Randomization) visit. At the Month 6 Treatment Period Visit, a -4 or +6 day visit window will be allowed in order to collect sanitary products from the last episode of menstrual bleeding or spotting prior to the Month 6 visit if ObbvieElagolix (ABT-620)
M12-815 Protocol Amendment 3

menstrual bleeding starts immediately prior to or coincides with the scheduled visit. The subject will be instructed to continue taking study drug from the extra blister card until she returns for the Month 6 visit.

Specific assessment-related visit windows are allowed. Please refer to Table 1, Visit and Assessment Windows, for assessment-specific visit windows.

1 able 1. Visit and Assessment windows	Table 1.	Visit and Assessment Windows
--	----------	------------------------------

Study Visit Windows				
Study Visit	Visit Windows			
Day 1 (Days 1 – 10 of the start of menses)	No visit windows*			
Treatment Period: Months 1 – 5	±4 days			
Treatment Period: Month 6	-4 or +6 days			
Post-Treatment Follow-Up Period: Months 1 – 12	±7 days			
Assessment-Specific Windows for Treatment and Post-Treatment Period				
Study Visit/Assessment	Visit Windows			
Treatment Period				
Day 1: Ultrasound	±7 days			
Day 1: MRI (if participating in MRI subset)	±7 days (unless an MRI was required in Screening. If MRI required in Screening, the Day 1 MRI will not be performed)			
Month 3: Ultrasound	±7 days			
Month 6: Ultrasound, MRI (if participating in MRI subset) DXA Scan and endometrial biopsy	-15 or + 4 days			
Post Treatment Follow-Up Period	·			
Month 3: Ultrasound, MRI (if participating in MRI subset)	-15 or +4 days			
Month 6: Ultrasound, DXA Scan	-15 or +4 days			
Month 12: DXA Scan	-15 or +4 days			

* Randomization must occur between Days 1 - 10 of the onset (first day of full menstrual flow) of menses.

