If a subject is known to have an endometrial $polyp \ge 1$ cm, and desires to have the polyp removed outside of the study, prior to entering Screening the subject must have a negative pathology report and return to one normal menses prior to screening.

Subjects who have qualifying uterine fibroids and uterine volume as assessed by ultrasound; however, have SIS images which are unable to fully assess the endometrial cavity, may undergo additional imaging modalities such as MRI for further evaluation.

An SIS may be performed during the Treatment Period if there is an intracavitary finding on ultrasound or MRI.

Magnetic Resonance Imaging (MRI) Subset:

[figure not shown]
A subset of subjects who consent to participate in the MRI Subset will have an MRI performed at the Day 1 (unless an MRI was performed in Screening as indicated below) and Month 6 or Premature Discontinuation visits during the Treatment Period and at the Post-Treatment Follow-Up Month 3 or Post-Treatment Premature Discontinuation Visit.

If the Day 1 MRI cannot be performed within the specified assessment window per Table 1, the MRI should not be performed and the subject will not participate in the MRI Subset. Subjects who have qualifying uterine fibroids and uterine volume as assessed by ultrasound; however, have SIS images which are unable to fully assess the endometrial cavity, may undergo additional imaging modalities such as MRI for further evaluation in Screening.

Subjects who had an MRI prior to Day 1 and agree to be part of the MRI subset, will not have an MRI repeated at Day 1; instead, subjects will have MRIs performed at the Month 6 visit during the Treatment Period and at the Post-Treatment Follow-Up Month 3 Visit.

Assessments for the MRI include, but are not limited to the following:

- Fibroid volume in cubic centimeters (of 3 largest fibroids)
- Fibroid location
- Uterine volume in cubic centimeters
- Presence of adenomyosis (diffuse adenomyosis as the dominant condition versus focal)

• Presence of any concerning findings

If the subject prematurely discontinued prior to Month 3, i.e., received < 3 months of study drug during the Treatment Period, an MRI will not be performed at the Premature Discontinuation visit during the Treatment or Post-Treatment Follow-Up Period.

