7.2 Definitions of Final Month and Final Visit

Final Month is defined as the last 28 days prior to and including the Reference Day, which is defined as the last visit date in the treatment period (last treatment visit date) or the last dose date if there is evaluable Alkaline Hematin (AH) data after the last treatment visit date and prior to or on the last dose date.

Final Visit is defined as the last non-missing assessment during the Treatment Period.

Post-Treatment Final Visit is defined as the last non-missing assessment during the Post-Treatment Follow-up Period.

7.3 Definition of Study Days (Days Relative to the First Dose of Study Drug) and Study End Days (Days Relative to the Last Dose of Study Drug)

For randomized subjects who received at least one dose of study drug, the study day is defined as the number of days since (positive values) or prior to (negative values) the first study drug dose. The day of the first study drug dose is defined as Study Day 1 while the last day prior to the first dose of study drug is defined as Study Day -1. There is no Study Day 0. Study end days are calculated based on the number of days relative to the last dose of study drug. The first day following the last dose of study drug is defined as Study End Day 1.

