7.4.3 Details Regarding Visit Windows

For analyses in the Treatment Period, time points and corresponding time windows are defined based on the time of exposure to study drug starting from Study Day 1.

The time windows described in this section will not be applied to bleeding assessments including AH data and Uterine Bleeding Questionnaire (UBQ). Rules described in Section 7.4.1 and Section 7.4.2 will be applied prior to defining time windows. Data considered as in the Treatment Period are not considered in the Post-Treatment Follow-up

Period as described in Section 7.4.1 and Section 7.4.2. Any data considered as Baseline (see Section 7.1) will not be included in any post-baseline windows.

Table 1 will be used for analyses of endpoints collected monthly in the Treatment Period and Post-Treatment Follow-up Period.

Table 1. Analysis Time Windows for Non-Bleeding Measurements Collected Monthly

Visit	Nominal Day (Study Day)	Time Window (Study Days)
Month 1	28	> 1 – ≤ 42
Month 2	56	> 42 – ≤ 70
Month 3	84	> 70 – ≤ 98
Month 4	112	> 98 – ≤ 126
Month 5	140	> 126 – ≤ 154
Month 6	168	> 154 – ≤ 196

	Nominal Day (Study End Day)	Time Window (Study End Days)
Post-Treatment Month 1	28	> 3 – ≤ 42
Post-Treatment Month 2	56	> 42 – ≤ 70
Post-Treatment Month 3	84	> 70 – ≤ 98
Post-Treatment Month 4	112	> 98 – ≤ 126
Post-Treatment Month 5	140	> 126 – ≤ 154
Post-Treatment Month 6	168	> 154 – ≤ 182
Post-Treatment Month 7	196	> 182 – ≤ 210
Post-Treatment Month 8	224	> 210 – ≤ 238
Post-Treatment Month 9	252	> 238 – ≤ 266
Post-Treatment Month 10	280	> 266 – ≤ 294
Post-Treatment Month 11	308	> 294 – ≤ 322
Post-Treatment Month 12	336	> 322 – ≤ 366

Table 2 will be used for analyses of endpoints collected every 3 months in the Treatment Period. If there is a scheduled Month 1 visit for the endpoint (e.g., PGIC-MB and

PGIC-NBUFS), the first subtable will be used. If there is no scheduled Month 1 visit for the endpoint (e.g., TAU/TVU, creatinine phosphokinase, urinalysis, apolipoprotein A and B, UFS-QoL), the second subtable will be used.

Table 2. Analysis Time Windows for Non-Bleeding Measurements Collected Every 3 Months in the Treatment Period

Visit	Nominal Day (Study Day)	Time Window (Study Days)
Month 1	28	> 1 – ≤ 56
Month 3	84	> 56 – ≤ 112
Month 6	168	> 112 – ≤ 196

Visit	Nominal Day (Study Day)	Time Window (Study Days)
Month 3	84	> 1 – ≤ 112
Month 6	168	> 112 – ≤ 196

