7.4.4 Handling of Multiple Assessments in a Specific Time Window

For all parameters except MBL volume, multiple assessments in a specific time window will be handled as follows:

1. For parameters other than BMD, TVU/TAU, MRI, and WPAI data, if more than one assessment is included in a time window, then the assessment performed closest to the scheduled study day (i.e., the nominal day) will be used in the analyses. If more than 1 day is of equal proximity to the nominal day, then the data collected after the nominal day will be used in the analyses.
2. For BMD, TVU/TAU, and MRI data, if multiple assessments exist in a specific time window, analyses of data will be based on the most conservative (worst) assessment.

3. For WPAI data, if multiple assessments exist in a specific time window in the treatment period, analyses of data will be based on the last assessment during the treatment period.

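### A Day 1 ultrasound done on Study Days 2 to 8, as the protocol allows, is analysed as a Month 3 scan; for MRI only a Day 8 scan is misplaced

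*SAP*

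**What the plan says.** **Protocol.** Table 1 in section 5.1 gives the assessment window as "Day 1: Ultrasound ±7 days". The MRI entry, "Day 1: MRI (if participating in MRI subset"), has the same ±7 days, with one restriction: "If MRI required in Screening, the Day 1 MRI will not be performed". Section 5.3.1.1 repeats the restriction: a woman in the subset who already had an MRI "will not have an MRI repeated at Day 1". The Synopsis and Appendix C schedule the Day 1 ultrasound for all subjects.

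**SAP, baseline.** Section 7.1 takes the baseline for uterine volume, fibroid volume and endometrial thickness from the last Screening Period measurement. A post-dose scan is allowed only if nothing was measured by Study Day 1, and then "the first measurement collected prior to Study Day 8 (Study Day 8 is not included) will be used as Baseline". Section 7.3 sets the day count: "The day of the first study drug dose is defined as Study Day 1", with no Day 0.

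**SAP, windows.** Under section 7.4.3, only data used as Baseline are kept out of post-baseline windows. The clause beginning "If there is no scheduled Month 1 visit for the endpoint (e.g., TAU/TVU" sends ultrasound to the second part of Table 2, where Month 3 covers days above 1 up to 112, with nominal Day 84. MRI uses Table 4, where days above 1 up to 140 are labelled Prior to Month 6.

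**SAP, several scans in one window.** Section 7.4.4 normally picks the assessment nearest the nominal day, but it exempts ultrasound, MRI and BMD. For these, "analyses of data will be based on the most conservative (worst) assessment".

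**The concern.** The protocol treats a scan within a week after first dose as a Day 1 scan. The SAP sorts it by Study Day, and the two documents use different cut-offs. An ultrasound meant to show the untreated state can then be filed as a three-month result. The rule for choosing among scans in a window does not prefer the one near Day 84, so the early scan can be the one analysed.

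The analyses exposed are the Month 3 ultrasound results:

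- the ANCOVA on change and percent change in primary fibroid, total fibroid and uterine volume (SAP 11.3.5.1);
- the logistic regression on a reduction of at least 25% (SAP 11.3.5.1);
- the ANOVA on endometrial thickness (SAP 12.7.2);
- the by-visit counts of significant ovarian cysts (SAP 12.7.1), where a cyst seen in the first week could be reported as a Month 3 finding.

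For MRI the stake is a missing volume baseline, which removes the woman from the change-from-baseline analysis.

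**Working it through.** The plan states no figure to reproduce here. The check is day arithmetic followed by classification under the SAP rules.

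**1. The allowed days.** First dose is Study Day 1 and there is no Day 0. Seven days later is 1 + 7 = Study Day 8, and seven days earlier is Study Day -7. The protocol window is therefore Study Days -7 to 8.

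**2. Whether the baseline fallback runs.**

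- *Ultrasound.* Inclusion criterion 3 requires a centrally assessed ultrasound, done in Screening or in Washout (Protocol 5.2.1 and 5.3.1.1). A scan before Study Day 1 therefore exists for every randomized woman, and the fallback condition is false.
- *MRI.* A Day 1 MRI is scheduled only when there was no earlier MRI, so the fallback condition is true.

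**3. Where a post-dose Day 1 scan goes.**

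| Scan done on | Ultrasound, earlier scan on file (normal case) | Ultrasound, none on file | MRI, none on file |
|---|---|---|---|
| Days 2 to 7 | Month 3 | Baseline | Baseline |
| Day 8 | Month 3 | Month 3 | Prior to Month 6 |

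The ultrasound problem thus comes from the Screening Period baseline rule together with a Month 3 window that opens on Day 2. The Day 8 cut-off in the fallback sentence causes only the MRI gap.

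**4. Which value is analysed.**

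- *Two ultrasounds in the Month 3 window.* The nearest-day rule would have rejected the early scan: Day 8 is 84 - 8 = 76 days from nominal, whereas the scheduled Month 3 ultrasound is allowed within 7 days of its visit. That rule does not apply to ultrasound, so the worst value is used. The SAP does not define worst for a volume; larger is the natural reading.
- *One ultrasound in the window.* Appendix C does not require a discontinuation ultrasound for a woman who stops before Month 3. Her Day 2 to 8 scan can then be her only Month 3 value.

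**5. Two related gaps in SAP 7.1.** The main rule refers to the Screening Period, but the fallback condition refers to Study Day 1. Consider a woman whose only earlier ultrasound was in Washout (Appendix C says it is not repeated in Screening) and whose Day 1 scan is done on Days 2 to 8. Read literally, she has no baseline: nothing was measured in Screening, and the Washout scan blocks the fallback. Separately, the adenomyosis fallback accepts scans before Study Day 15, so one scan can be Baseline for adenomyosis but not for volume.

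**6. Illustration of size only.** Every input here is assumed; none is in the documents. Take worst as the larger volume, a true Month 3 reduction of 25% on active and 0% on placebo, and a share f of women in each arm with a Day 2 to 8 scan.

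Without measurement error the early scan always wins on active, and the difference becomes -25 × (1 - f):

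- f = 0.10: -22.5 points
- f = 0.30: -17.5 points
- f = 0.50: -12.5 points

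With measurement error, taking the larger of two scans also lifts the placebo values a little, so the shrinkage is smaller. A simulation with a 10% log-scale SD gave the following.

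| f | Difference, real Month 3 scan only | Difference, worst-value rule | Active arm with at least 25% reduction |
|---|---|---|---|
| 0.10 | -25.3 | -23.3 | 50% to 45% |
| 0.30 | -25.3 | -19.4 | 50% to 36% |
| 0.50 | -25.3 | -15.4 | 50% to 26% |

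Across SDs of 5% to 20%, true reductions of 15% or 25% and the same three shares, the difference shrank by about 6% (15.6 to 14.7) to 45% (25.1 to 13.9).

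**The case against.** The best defence is that little depends on this. The ultrasound belongs to the Day 1 visit, and most scans may be done at or before it. Read sensibly, SAP 7.1 accepts any scan through Study Day 1 as baseline, so only late scans are affected. The analyses concerned are unranked efficacy or safety summaries, and for volumes the likely bias is against the drug. The cut-off before Day 8 is also used for some questionnaires, so it looks like a deliberate convention.

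Most of this stands, and it is why the point is minor. It does not remove the defect, because nothing in the SAP keeps a Day 2 to 8 ultrasound out of Month 3. Whatever its purpose, the convention is one day short of the protocol's MRI window.

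A reader might infer three stronger things that the documents do not support:

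- *That post-dose MRIs are generally rejected as baseline.* They are not. A Day 1 MRI is done only when no earlier MRI exists, so Days 2 to 7 are accepted.
- *That MRI also contaminates Month 3.* It cannot. MRI has no Month 3 window in Table 4, and SAP 12.7 limits the Month 3 imaging summary to ultrasound.
- *That close to half of the Day 1 scans are affected, because seven of the fifteen allowed days (-7 to -1 and 1 to 8) fall after Day 1.* That counts calendar days. The documents give no share of scans done on those days.

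**Conclusion.** The point holds for ultrasound on Days 2 to 8 and, for MRI, on Day 8 alone. Followed as written, the plan can report a scan taken after at most about a week of treatment as a Month 3 result, either by choosing it as the worst value or because it is the only scan in the window.

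If worst means larger and the drug shrinks fibroids, the Month 3 volume and 25%-reduction comparisons are biased toward no effect. Endometrial thickness and ovarian cyst results at Month 3 can also be contaminated, with no direction that can be fixed in advance. The size cannot be derived from the documents; the figures in the illustration show direction and scale under assumed inputs and are not an estimate for this trial.

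Month 6 imaging is unaffected, since its windows open after Day 112 for ultrasound and after Day 140 for MRI. The primary and ranked secondary endpoints use no imaging. Severity is minor.

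**What to change.** Two changes are needed.

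1. In SAP 7.1, define the imaging baseline as the last scan on or before Study Day 1, including a Washout scan; if there is none, use the first scan through Study Day 8 inclusive. This closes the Day 8 MRI gap and the Washout-only gap.
2. In SAP Table 2, start the Month 3 ultrasound window after Study Day 8, so that no protocol-allowed Day 1 scan can count as Month 3.

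The first change alone does not help ultrasound: with an earlier scan on file the fallback still does not run, and Days 2 to 8 would still fall in Month 3. While section 7.4.4 is open, it should also state which direction is worst for volume and for endometrial thickness.

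The cost is SAP wording and window code. No visit, procedure or data collection changes.
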